#### Schedule for individual participants from recruitment to follow-up:

**Tasks and Data Collected during Assessment and Probes:**

TIMING	Screener	Assessment	Phase: A1 Baseline Pre-treatment Baseline Probes	Phase: B Treatment Probes	Phase: A2 Baseline post-treatment		Phase C: Four week follow up
					Post-treatment Assessment	Maintenance Probes	
TASKS		1-2 visits	three times weekly across baseline period	1st and 3rd therapy session each week,	same day as the 1st maintenance probe	three times weekly across the baseline period	once, 4 weeks after the last therapy session
Screening (Questionnaire of demographic Information and inclusion/exclusion criteria)	X						
Timed Water Swallow Test (Hughes & Wiles, 1996; Sarve et al., 2021) (Video Recording)		X	X	X	X	X	X
Test of Mastication and Swallowing Solids (Athukorala et al., 2014; Huckabee et al., 2018) (Video Recording)		X	X	X	X	X	X
Information regarding time taken to complete meal and IDDSI Level (Cichero et al., 2017) (Images of food, Questionnaire)		X	X	X	X	X	X
Clinical Swallow Evaluation with Ultrasound using the MBSImp Rating Scale (Martin-Harris et al., 2008) for oral phase components (Video recording)		X	X	X	X	X	X

Swallowing Quality of Life Questionnaire (SWAL-QoL) (Questionnaire) (McHorney et al., 2002)		X				X		X
Theoretical Framework of Acceptability Questionnaire (Sekhon, Cartwright & Francis, 2022) (Questionnaire)						X		
Maximum Phonation Time (MPT) (Speyer et al., 2010) (Audio Recording)		X	X	X	X	X	X	X
Swallowing Disturbance Questionnaire (SDQ-PD) (Manor et al., 2007) (Questionnaire)	X					X		X
30 second monologue (Audio Recording)		X	X	X	X	X	X	X
North Wind and the Sun passage (Amundsen & Hansen, 2014) (Audio Recording)		X				X		X
Picture description (Audio Recording)		X				X		X
Rate at which participants can accurately repeat a series of rapid, alternating sounds as per published normative data (Kent, Kim & Chen, 2022) (Video Recording)		X	X	X	X	X	X	X

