## Probes

As shown on page 8, Probes for Phase A1 and A2: The TWST and TOMASS and a measurement of maximum phonation time and a 30 second monologue will be obtained 6 times for those allocated in the 2-week baseline periods and 9 times for those allocated in the 3-week baseline period.

Probes for Phase B: Treatment probes will be taken twice weekly (on the day of the first and last therapy session each week) for 4 weeks. Treatment probes will be identical to the baseline probes and will be collected immediately before therapy commences on that day.

The probes will take approximately 30-40 minutes and breaks will be provided if a participant experiences fatigue.

After the end of Phase B, a repeat assessment will be completed (identical to the one conducted at the start of the treatment program) by a qualified speech pathologist. Participants will also be asked to complete a Theoretical Framework of Acceptability Questionnaire to understand their acceptance and the feasibility of the intervention.

As this is a pilot, the frequency and duration of the treatment sessions, the duration and frequency of breaks provided, the type of foods and fluids used, the amount and type of feedback provided and the number of times the participant is asked to swallow and sets of swallows may be altered based on participants' fatigue level and response to the therapy protocol.

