### **6.3 Population/ Calculation of sample size**

Sample size calculation: This is a phase 1 study to acquire data for a sample size calculation. Considering no protocol exists for ultrasound visual feedback in dysphagia rehabilitation in people with Parkinson's, the researchers will first aim to assess the feasibility of use with a single participant. Subsequently, n=6 will be recruited to allow for attrition expected in behavioural rehabilitation. This follows a similar sample size to other pilot studies (Blyth, McCabe, Madill, & Ballard, 2017).

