### **6.14 Statistical analyses**

As per standard procedure for single case within participant studies, experimental and control measures will first be graphed and visually inspected for change. If the visual inspection indicates change over time, statistical analysis will be completed. As multiple, repeated measures will be taken for each participant, the data will first be analysed for correlations. If the correlation coefficient was not significant, the assumption of independence in measurements will be made, and effect sizes within participant will be calculated using  $d_2$  as this measure is appropriate for single case data (Beeson & Robey, 2006).

In the presence of serial dependency between data points, the data will be analysed using percent of nonoverlapping data (PND) (Scruggs, Mastropieri & Casto, 1987). PND is a commonly used calculation to measure change in measures taken across research phases. The highest data point in the baseline (A1) phase is compared across all research phases. The number of data points either above or below that value is calculated as a percentage of the total number of data points. The higher the number of nonoverlapping data points, the stronger the effect.

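### A significance test for correlation decides between d2 and PND; on a short phase it has little power, and on the whole series the treatment effect itself sets it off

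*Protocol*

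**What the plan says.** Protocol section 6.14 starts with graphs and visual inspection. Where these suggest change, statistics follow: "the data will first be analysed for correlations". A non-significant result leads to one branch: "If the correlation coefficient was not significant, the assumption of independence in measurements will be made". In that branch the measure is d2, worked out separately for each participant. The other branch reads: "In the presence of serial dependency between data points, the data will be analysed using percent of nonoverlapping data (PND"). No alpha, lag or span of the series is given for the test. No measure is named that every series will receive whichever branch it takes.

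The Probes section sets the series length. Baseline and post-treatment probes are taken "6 times for those allocated in the 2-week baseline periods and 9 times for those allocated in the 3-week baseline period", and treatment probes twice weekly for four weeks. Section 6.3 gives the purpose: "This is a phase 1 study to acquire data for a sample size calculation".

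**The concern.** Failing to find a correlation in a short series is weak evidence that there is none. If the test rarely detects dependence, d2 will be calculated as if probes were independent when they may not be, and its apparent precision will be too good. If the test is instead run across phases, a genuine improvement makes neighbouring points alike and looks like dependence, so the clearest responders would be the ones moved to PND. Moving them cures nothing, because PND counts points beyond one extreme baseline value and makes no allowance for autocorrelation. The rule governs the effect estimate for both primary outcomes and every control measure, and it can leave some series in SD units and others in percent.

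**Working it through.** **Inputs from the protocol.** A1 and A2: 3 probes per week × 2 or 3 weeks = 6 or 9 each, which agrees with the stated counts. Phase B: 2 per week × 4 weeks = 8. Whole series: 6 + 8 + 6 = 20 or 9 + 8 + 9 = 26; one follow-up probe makes 21 or 27. Series on the primary outcomes: 6 participants × 2 outcomes = 12.

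**Assumptions, because the protocol gives none.** Lag 1, two-sided 0.05, stationary AR(1) errors with autocorrelation φ. Results come from simulation (40,000 to 100,000 series per setting).

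**Reading 1: test within a phase.** For Pearson r on m = n − 1 lagged pairs, the critical value is t/√(m − 2 + t²), with t on m − 2 degrees of freedom:

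- n = 6, m = 5: 3.182/√(3 + 10.13) = 0.88
- n = 9, m = 8: 2.447/√(6 + 5.99) = 0.71

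The mean estimated lag-1 autocorrelation at φ = 0.5 is only 0.03 (n = 6) or 0.17 (n = 9), far below these thresholds. Percentage of series declared significant:

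| Probes | φ | ±1.96/√n bound | Pearson | Size-exact |
|---|---|---|---|---|
| 6 | 0 | 0.7 | 2.3 | 5 |
| 6 | 0.5 | 0.2 | 2.4 | 11 |
| 6 | 0.7 | 0.1 | 4 | 16 |
| 8 | 0.5 | 0.6 | 4 | 17 |
| 9 | 0 | 1.8 | 2.7 | 5 |
| 9 | 0.5 | 2.0 | 5 | 20 |
| 9 | 0.7 | 5 | 13 | 32 |

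Even the most favourable version misses φ = 0.5 in 80% or more of series.

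**Reading 2: test on the whole series.** Power at φ = 0.5 is better: 36-52% with 20 points and 56-68% with 27. The test also responds to the treatment effect. With fully independent errors (φ = 0) and the Pearson test, the percentage flagged as dependent is as follows. Each range runs from a step change after A1 to a gradual change over B held in A2.

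| True gain | 20 points | 26 points |
|---|---|---|
| none | 4 | 4 |
| 2 SD | 36-39 | 57 |
| 3 SD | 77-83 | 94-95 |

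**What a missed dependence can do (illustration).** Take d2 as A2 minus A1 over the pooled within-phase SD, with no treatment effect. The percentage of series with |d2| > 1 is:

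| Probes | φ = 0 | φ = 0.5 | φ = 0.5, A1 test not significant |
|---|---|---|---|
| 6/8/6 | 11 | 36 | 36 |
| 9/8/9 | 5 | 26 | 26 |

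Passing the test gives no protection. PND is affected too: with no effect, the chance that at least half of the phase B points fall beyond the best A1 point rises from 7% to 16% (6 baseline probes) and from 3% to 9% (9 baseline probes) as φ goes from 0 to 0.5.

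**Mixed scales.** If each of the 12 series is flagged with probability p, independently, the chance that both measures appear is 1 − p¹² − (1 − p)¹². With p = 0.025 this is 1 − 0.975¹² ≈ 26%. With per-phase Pearson testing at φ from 0.3 to 0.5 it is about 21-47%.

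**The case against.** The strongest defence is that this is a pilot with six participants. It relies on visual analysis first, has concurrent control measures, and uses effect sizes as description without any significance decision on efficacy. The span, lag and alpha could be settled in an analysis plan that is not shown. All of this is fair and lowers the severity. It does not rescue the rule, which the protocol itself states: settling the span only chooses which of the two failures applies. The two failures are alternatives and should not be added together.

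Several stronger inferences go beyond the documents:

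- **That the test has no power at all.** Its performance depends on the version. With size-exact critical values it reaches 16% (6 probes) or about 32% (9 probes) at φ = 0.7, which is poor but not nil.
- **That results will certainly be split between two scales.** They may be. If no series is flagged, all are on d2.
- **That the plan wrongly combines participants.** Section 6.14 specifies within-participant effect sizes, and no pooling is planned.
- **That 36% and 26% are this plan's error rates.** The contrast, the d2 formula and the cut-off of 1 are assumptions, and neither the visual screening nor the control measures were modelled.
- **That a later trial would be undersized by a known factor.** Section 6.3 does not say that d2 or PND will be the input, and raw primary-outcome values are collected at every probe, so a between-participant SD can still be calculated.

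**Conclusion.** The decision rule in section 6.14 is unsound on either reading. Per phase, non-significance says little about independence: at an autocorrelation of 0.5, detection is about 0.2-11% with 6 probes and 2-20% with 9. Over the whole series, the size of the effect helps choose the metric: about 36-57% of series are flagged at a 2-SD gain and 77-95% at 3 SD, with no dependence present. The alternative measure does not address the problem that triggers it. These figures rest on lag 1, two-sided 0.05 and AR(1) errors, none of which the protocol states; the ranges cover the test versions, series lengths and shapes of change examined. The plan should be changed, but given the pilot aims, the descriptive use of effect sizes and the retained raw data, this is a should-fix point and does not invalidate the study.

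**What to change.** Reword section 6.14, before any results are seen, as follows:

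1. Delete the correlation test as a gate and the switch between measures.
2. Name in advance the same effect measure or measures for every participant and outcome. d2, a nonoverlap index, or both can stay, provided they are shown for all series alike.
3. Report the estimated autocorrelation descriptively, from residuals after removing phase means, so that the treatment effect does not inflate it.
4. Give the phase change in raw units (seconds, ml/s) with an interval that allows for autocorrelation whatever any test shows.
5. For section 6.3, report the between-participant SD of raw change with its confidence interval. With n = 6 the 95% limits are √(5/χ²) times the estimate, that is 0.62 to 2.45 times.

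A model pooled over participants with AR(1) errors is optional, and section 6.7.3 allows a data set as small as three. Adding a linear time term is a trade-off, because time and phase are nearly collinear. For 6/8/6 probes the per-person standard error of A2 minus A1 goes from √(2/6) = 0.58 to 1.70 SD with independent errors, and from 0.82 to 1.54 SD at φ = 0.5, so it about doubles to triples.

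The cost is a reworded section, modest extra analysis and wider intervals than independence would give. No new data are needed.

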### **4.2 Hypotheses:**

People with Parkinson's Disease with dysphagia who participate in a four-week intervention using ultrasound visual feedback and principles of motor learning will show improvements in their swallowing efficiency (i.e., reduction in time taken to swallow liquid and food)

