### **6.5 Primary and Secondary Outcome Measures**

The primary outcome measures include:

- Timed Water Swallow Test (TWST) (Hughes & Wiles, 1996; Sarve et al., 2021)

- Test of Masticating and Swallowing Solids (TOMASS) (Athukorala et al., 2014; Huckabee et al., 2018)

Secondary outcome measures:

- Texture of food as per the International Dysphagia Diet Standardisation Initiative Level (IDDSI) (Cichero et al., 2017)
- Consistency of liquid as per the the International Dysphagia Diet Standardisation Initiative Level (IDDSI) (Cichero et al., 2017)
- Observational measures rated with an ultrasound probe under the chin.
  - Changes in components 2, 3, 4 and 5 listed on the Modified Barium Swallow Impairment Profile (MBSImp) (Martin-Harris et al., 2008) which is a rating scale that rates key physiological aspects of swallowing in the different phases. Components 2, 3, 4, and 5 are specifically related to the oral phase of swallowing.
  - Average time taken to swallow a single sip of liquid (ml/s)
  - Time taken to swallow (a) ½ biscuit (b) a dessert spoon of diced fruit and (c) a dessert spoon of puree
  - Number of times the participant needs to swallow to clear a single, controlled sip of liquid (number of swallows/ml)
  - Number of times the participant needs to swallow to clear (a) ½ biscuit (b) a dessert spoon of diced fruit and (c) a dessert spoon of puree from their mouth
- Patient reported measures:
  - Time taken to complete meals
  - Swallowing Quality of Life Questionnaire (SWAL-QoL) (McHorney et al., 2002)
  - Theoretical Framework of Acceptability based questionnaire (Sekhon, Cartwright & Francis, 2022)
  - Swallowing Disturbance Questionnaire - PD (SDQ-PD)

Control measures

- Maximum Phonation Time (Speyer et al., 2010)
- Speech Rate (Syllables per minute during a 30 second monologue)
- Average decibels in 30 second monologue
- Intelligibility Rating of monologue using the Frenchay-2 Rating scale (perceptual) (Enderby & Palmer, 2008)

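### PND is benchmarked on the highest baseline point for every measure, although for swallow times and counts the hypothesised benefit is a decrease

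*Protocol*

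**What the plan says.** Section 6.14 of the protocol graphs each measure first and goes on to statistics only if visual inspection suggests change. Series without significant correlation are summarised by the effect size d2. Serially dependent series are summarised by PND, defined in three steps:

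- Benchmark: "The highest data point in the baseline (A1) phase is compared across all research phases".
- Count: "The number of data points either above or below that value is calculated as a percentage of the total number of data points".
- Reading: "The higher the number of nonoverlapping data points, the stronger the effect".

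The hypothesis in section 4.2 is stated as a "reduction in time taken to swallow liquid and food". Section 6.5 lists outcomes that improve in different directions: times and numbers of swallows, which should fall, alongside control measures such as maximum phonation time. One secondary outcome is given as "Average time taken to swallow a single sip of liquid (ml/s", which names a time but carries the unit of a speed.

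Under Probes, the A1 and A2 measures are taken "6 times for those allocated in the 2-week baseline periods and 9 times for those allocated in the 3-week baseline period". For Phase B, "Treatment probes will be taken twice weekly (on the day of the first and last therapy session each week) for 4 weeks".

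**The concern.** PND asks how many later points lie beyond the best baseline value. For a measure that improves by rising, the best baseline value is the highest. For one that improves by falling, it is the lowest. Section 6.14 fixes the highest for all measures, and nothing elsewhere in the protocol switches it.

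For a swallow time, the highest A1 point is the slowest baseline trial. Every other A1 point, ties aside, also lies below it, so a Phase B point below it shows no separation between phases. The option of counting above or below changes the side, not the benchmark. Counting above the slowest baseline trial scores worsening as effect.

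PND is one of only two stated effect measures, and the only one for serially dependent data. The Synopsis predicts improvement in swallowing outcomes and none in control outcomes. If times are counted below the highest point and higher-is-better controls above it, that contrast could appear with no treatment effect at all.

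**Working it through.** The protocol gives no PND value, threshold or effect size, so there is no stated figure to reproduce. The check asks what the written rule returns when treatment does nothing.

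**Inputs from the protocol (Probes).** Baseline probes in A1: n = 6 or 9. Phase B probes: 2 per week × 4 weeks = 8.

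**Step 1: independent data, no effect.** One new point and n baseline points are exchangeable, so the new point is the largest of the n + 1 values with probability 1/(n + 1). Hence:

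- P(below the highest A1 point) = n/(n + 1)
- P(below the lowest A1 point) = P(above the highest) = 1/(n + 1)

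| | n = 6 | n = 9 |
|---|---|---|
| Below highest A1 | 6/7 = 85.7% | 9/10 = 90.0% |
| Below lowest A1 | 1/7 = 14.3% | 1/10 = 10.0% |

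**Step 2: serially dependent data, no effect.** These are the data that reach PND. The protocol gives no autocorrelation, so this step is an assumption: a stationary Gaussian AR(1) series, probes treated as equally spaced, coefficient phi from 0.3 to 0.8, 8 Phase B points, 200,000 simulated series. Mean share of Phase B points:

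| phi | n = 6, below highest | n = 6, below lowest | n = 9, below highest | n = 9, below lowest |
|---|---|---|---|---|
| 0.3 | 83% | 17% | 88% | 12% |
| 0.5 | 81% | 19% | 86% | 14% |
| 0.8 | 75% | 25% | 81% | 19% |

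The median share below the highest point is 87.5% (n = 6) and 100% (n = 9) at each of these phi values.

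**Step 3: worsening.** If a participant's times rise by 0.5 SD in Phase B, the share below the highest A1 point is still 74% (n = 6) or 80% (n = 9) for independent data. For phi 0.3 to 0.8 it is about 58-71% or 66-78%.

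**Step 4: the other side.** For a true 2-SD reduction with independent data, counting above the highest A1 point gives 0.3% (n = 6) or 0.1% (n = 9). Counting below the lowest gives 73% or 67%.

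**Step 5: the denominator.** The text does not say whose points make up the total. Steps 1 to 4 divide by Phase B points only. If A1 points enter both numerator and denominator, the null value in Step 1 barely moves: (5 + 8 × 6/7)/14 = 84.7% and (8 + 8 × 9/10)/17 = 89.4%. If A1 points enter the denominator only, it falls to (8 × 6/7)/14 = 49.0% and (8 × 9/10)/17 = 42.4%. The same data can therefore give quite different percentages.

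**The case against.** Several points can fairly be made for the plan.

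- **The highest point is right for some measures.** It suits anything that improves by rising, such as phonation time or a rate in ml/s. The protocol also does not say which Timed Water Swallow Test or TOMASS metric will be analysed. This stands: the error is certain only for metrics expressed as times or counts.
- **Independent data never reach PND.** A reader might infer that an ineffective treatment will score 86-90%. The document does not support that as the general figure, because such data go to d2. The relevant figures are those in Step 2, which are lower and rest on an assumed model. They do not change the conclusion.
- **Flat series may be stopped by visual inspection.** This also stands in part. The step may remove some null series, but it does not repair the index for those that pass.
- **The side would follow the expected direction.** That is the natural reading of above or below, and it makes the near-zero result in Step 4 unlikely in practice. It is also the reading under which overlap is counted as effect.
- **A capped maximum.** A reader might infer that putting all points in the denominator caps a perfect effect at 15/21 = 71% or 18/27 = 67%. That needs A1 points left out of the numerator. Counted below the highest A1 point over all phases (6 + 8 + 6 + 1 or 9 + 8 + 9 + 1 points), a perfect effect scores 20/21 = 95% or 26/27 = 96%. The cap is not a property of the rule as written.
- **Scale of the study.** PND here is a conditional, descriptive index in a pilot of six, the raw data are graphed, and no success threshold is set. This limits the consequences but does not make the definition correct.

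**Conclusion.** The rule is wrong as written for outcomes where lower is better. With no treatment effect, counting below the highest A1 point gives a mean of about 75-83% (6 probes) or 81-88% (9 probes) in serially dependent data. The lowest-point benchmark gives about 17-25% or 12-19%. Because the protocol reads a higher percentage as a stronger effect, the written rule can present ordinary overlap, or mild worsening, as a strong result on the quantity named in the hypothesis.

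The direction of the error follows from sections 4.2 and 6.14 alone. The size rests on the assumed AR(1) model with phi 0.3 to 0.8, on the below-highest count, and on a Phase B denominator. The independent-data values of 86% and 90% are exact but describe data the protocol sends to d2.

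A reader might also ask how often a null series would pass a 70% cut-off. Purely as an illustration, under the same AR(1) range this happens in 67-80% (n = 6) or 75-88% (n = 9) of series with the written benchmark. With the lowest point it is about 3-13% or 1-9%. The protocol sets no such threshold, so these are not error rates of the trial. They also show that the corrected index is not free of chance findings under serial dependency.

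**What to change.** Reword section 6.14 so that the benchmark follows the direction of benefit:

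1. Lower-is-better measures: take the lowest A1 value and count points below it.
2. Higher-is-better measures: take the highest A1 value and count points above it.
3. Use as denominator only the points of the phase being compared, and report Phase B and Phase A2 separately.
4. In section 6.5 and the Synopsis, state for each outcome the metric analysed, its unit and the direction that counts as improvement.
5. Reconcile the single-sip measure: either a time in seconds (or s/ml), or a swallowing speed in ml/s.

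The cost is a few sentences and a short table. No extra data, visits or participants are needed. The change should be made before any outcome data are examined, so that the choice of benchmark cannot be influenced by the results.

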### **Allocation to Baseline Phase:**

Once enrolled in the study, participants will be randomly allocated to varying baseline duration through a computer-generated block randomisation.

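### PND is scored against one extreme baseline point, so its expected value depends on whether a participant was randomised to 6 or 9 baseline probes

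*Protocol*

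**What the plan says.** Under Allocation to Baseline Phase, the protocol states that "participants will be randomly allocated to varying baseline duration through a computer-generated block randomisation". The Probes section sets the resulting number of measurements in phases A1 and A2: "6 times for those allocated in the 2-week baseline periods and 9 times for those allocated in the 3-week baseline period". For Phase B, "Treatment probes will be taken twice weekly (on the day of the first and last therapy session each week) for 4 weeks", which makes 8.

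Section 6.14 starts with visual inspection. If that suggests change and the measurements can be treated as independent, the within-participant effect size is d2. Otherwise, "In the presence of serial dependency between data points, the data will be analysed using percent of nonoverlapping data (PND"). The reference value is a single baseline point: "The highest data point in the baseline (A1) phase is compared across all research phases". The score is then defined: "The number of data points either above or below that value is calculated as a percentage of the total number of data points". The section ends by equating more nonoverlap with a stronger effect. The protocol does not equalise the number of A1 points used, adjust PND for baseline length, or caution against comparing participants with different baselines.

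**The concern.** PND compares each later point with the most extreme of the A1 points. The expected extreme moves outwards as points are added, so the hurdle is higher after 9 probes than after 6. The rule that a higher PND means a stronger effect is therefore not valid between the two groups that the trial's own randomisation creates.

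The longer baseline, which gives more information, would tend to show the smaller effect. The expected PND without any effect is also above zero and differs between the groups, so a small PND can be mistaken for a response. With about six participants, individual results will naturally be set beside each other. Section 4.1 makes effectiveness an aim, and section 6.3 says that the data will inform a later sample size calculation.

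**Working it through.** The protocol gives no PND value, threshold or error rate, so there is no figure of its own to reproduce.

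**Inputs from the protocol**
- A1 probes: n = 6 or 9 (Probes).
- Phase B probes: 2 per week × 4 weeks = 8 (Probes).
- Improvement on the timed outcomes is a reduction in time (section 4.2).

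**Assumptions**
- Normal data with a constant shift of d baseline SDs in Phase B.
- Lag-1 correlation of 0, 0.3, 0.4 or 0.6.
- PND is the share of Phase B points beyond the best A1 point in the direction of improvement, which for a timed outcome is the lowest A1 value.

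**No effect, exchangeable points.** A given Phase B point is equally likely to hold any rank among itself and the n baseline points. Expected PND is therefore 1/(n + 1), whatever the distribution: 1/7 = 14.3% and 1/10 = 10.0%.

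**With a shift, independent normal points.** Expected PND = ∫ φ(x − d) Φ(x)^n dx, integrated numerically. The all-pairs index NAP is the share of A1–B pairs in which the B value is the better one. Its expectation is Φ(d/√2), which does not contain n.

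| Shift d (SD) | PND, 6 probes | PND, 9 probes | Gap (points) | NAP, 6 or 9 probes |
|---|---|---|---|---|
| 0 | 14.3% | 10.0% | 4.3 | 50% |
| 0.5 | 26.1% | 19.9% | 6.2 | 64% |
| 1 | 41.4% | 34.1% | 7.3 | 76% |
| 1.5 | 58.1% | 50.9% | 7.2 | 86% |
| 2 | 73.3% | 67.4% | 5.9 | 92% |
| 3 | 92.6% | 90.2% | 2.4 | 98% |

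**With serial dependency**, the only setting in which section 6.14 uses PND (simulation of 200,000 AR(1) series, 8 Phase B points):

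| Lag-1 correlation | No effect, 6 vs 9 | 1 SD shift, 6 vs 9 |
|---|---|---|
| 0.3 | 16.6% vs 11.6% | 44.6% vs 36.9% |
| 0.4 | 17.7% vs 12.5% | about 46% vs 38% |
| 0.6 | 20.7% vs 15.1% | 50.8% vs 42.8% |

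Positive correlation raises the chance level in both groups and leaves the gap in place. At a correlation of 0.4 and a 1 SD shift, mean NAP is about 76% in both groups.

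**Spread in one participant.** With 8 points, PND moves in steps of 100/8 = 12.5 points. At correlations of 0 and 0.4 its SD is roughly 13 to 30 points, depending on the shift.

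**Literal wording.** If points below the highest A1 value are counted for a timed outcome, expected PND at no effect with independent points is 1 − 1/7 = 85.7% against 1 − 1/10 = 90.0%. The dependence on baseline length remains, with its direction reversed.

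**The case against.** The strongest reply is that section 6.14 describes effects within a participant, for whom baseline length is fixed, and that no pooling, ranking or formal comparison of PND between participants is planned. That is correct. It limits the consequence to side-by-side reading and informal summary, and to the non-zero chance level within each participant.

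The remaining objections set further limits:
- PND is a fallback, reached only after visual inspection suggests change and serial dependency is found. The figures above do not model the visual step.
- The gap is one of expectation. A reader might infer that two participants with the same response will receive different PND values. With 12.5-point steps and an SD well above the gap, they need not.
- A reader might infer that the longer baseline is always penalised. That holds for scoring in the direction of improvement; the literal reference to the highest point reverses it for timed outcomes. Which extreme serves as the reference for each measure is a separate matter that the protocol should also settle.
- A reader might put a false-positive rate on PND, for instance the chance of reaching 50%. The protocol states no such cut-off, so no error rate can be attributed to the plan.
- An all-pairs index is not immune to serial dependency. At no effect and a correlation of 0.4, an independence-based NAP test at nominal 5% rejected in about 15.0% (6 probes) and 16.5% (9 probes) of simulated series. NAP equalises the expected value, not the whole chance distribution.
- PND is a cited and commonly used index, so preferring another is partly a choice of method.

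None of this removes the dependence of PND on the randomised baseline length, and section 6.14 itself fixes both the index and the way it is read.

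**Conclusion.** The point stands as a cheap improvement to the analysis, not as an error that undermines the trial. For the same effect, expected PND in the direction of improvement is lower after 9 baseline probes than after 6. The gap is about 4 to 8 percentage points for no-to-moderate effects and about 2 points at 3 SD.

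The values 1/7 and 1/10 at no effect need only exchangeable points. The other figures rest on the assumed normality, shift and lag-1 correlation. The protocol's equation of higher PND with stronger effect does not hold between participants with different baseline lengths, and in neither group does zero represent the chance level.

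**What to change.** In section 6.14, replace PND with an all-pairs index (NAP or Tau), or report one beside it, for A1 versus B and for A1 versus A2. Score it in each measure's stated direction of improvement. Any interval must allow for serial correlation, for example a block-based interval or one simulated from a fitted autoregressive model. An independence-based confidence interval would be wrong in the branch where independence has already been rejected.

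If PND is kept for continuity with earlier work, add two statements:
- Values from 6-probe and 9-probe participants are not directly comparable.
- With scoring in the direction of improvement, chance PND is at least 1/7 or 1/10 respectively, and higher under positive serial correlation. These are minimum chance levels, not exact null values.

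The change uses data already planned. It costs a revision of wording, slightly more analysis work for the interval, and a less direct comparison with older reports based on PND.
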